**Table 2. Aim 2 Open Pilot Measures**

Domain	Measurement Tool and Schedule
Demographic	Age/birth date; gender; biological sex; race/ethnicity; education level; employment status; marital status; household income; disability status; language fluency; people and/or children in the household; RUCA code (i.e., zip code); country of birth; country lived in prior to age 12; years lived in the US, parents' countries of origin; ethnic identity; languages spoken at home; assessment of English fluency. Pre
Clinical	
Type of pain; pain location and number; pain treatments; pain medications; cannabis use for pain; medical comorbidities; mental health conditions and medications. Pre and post, when applicable (chart review and self-report: pain, medication, and medical history questionnaire)
 
Tobacco, Alcohol, Prescription medications, and other Substance (TAPS); assess substance use behaviors. Pre, post

Other	
The Everyday Discrimination Scale – Short (EDS-S); assesses experiences of daily discrimination against minority populations. Pre, post
 
PROMIS Sleep Disturbance – Short Form 6a v1.0; assesses duration and quality of sleep. Pre, post
 
The Pittsburgh Sleep Quality Index (PSQI); assesses sleep quality. Using single item from this scale to assess sleep duration. Pre, post
 
Quota-based pacing questionnaire – assesses ability to engage in meaningful activities and increase activity level gradually. Weekly

Multimodal physical function	
PROMIS Physical Function – Short Form 6b v2.0; assesses one's ability to carry out activities that require physical actions, ranging from self-care to social and work. Pre, post
 
ActiGraph GT3X-BT; watch with blank screen that assesses average step count. Pre, post
 
Six-minute walk test (6MWT) – assesses distance walked in 6 minutes. Pre, post

Emotional function	
Generalized Anxiety Disorder – 7 (GAD); 7-item measure of anxiety symptoms. Pre, post
 
Patient Health Questionnaire – 8 (PHQ); 8-item measure of depressive symptoms. Pre, post
 
Perceived Stress Scale (PSS-4); assesses stress perception levels. Pre, post
 
The Post-Traumatic Checklist – 6 (PCL-C); assess current Post Traumatic Stress Disorder symptoms. Pre, post

	Contrast Avoidance Questionnaire – Shortened (CAQ-S) ; a measure of sustaining negative emotionality to protect against sudden shifts in emotion. Pre, post
Pain intensity	Brief Pain Inventory (intensity and interference) – Short Form (BPI) ; measures pain at its “worst,” “least,” “average,” and “now”. Pre, post  Patient Global Impression of Change (PGIC) ; measures fluctuations in pain. Post
Nonadaptive pain reactions	Pain Catastrophizing Scale (PCS) ; assesses magnification, helplessness, and rumination about pain. Pre, Post  The Pain, Enjoyment of Life, and General Activity Scale (PEG) ; brief measure of a participant’s self-reported pain intensity and pain interference. Pre, post  Tampa Kinesiophobia Scale (TSK) ; assesses fear of pain and activities that cause pain. Pre, Post
Loneliness	UCLA-3 Loneliness Scale ; assesses loneliness in relational connectedness, social connectedness and self-perceived isolation dimensions. Pre, post
Social support	Interpersonal Support Evaluation List (ISEL-12) ; assesses perceived availability to potential social resources. Pre, post
Adaptive coping	Self-Compassion Scale – Short Form (SCS-SF) ; assesses participants’ capacity for self-compassion. Pre, post  Gratitude Questionnaire (GQ-6) assesses individual differences in the proneness to experience gratitude in daily life. Pre, post  Applied Mindfulness Process Scale (AMPS) ; assesses how participants’ use mindfulness when facing challenges in daily life. Pre, post  Cognitive and Affective Mindfulness Scale – Revised (CAMS-R) ; measures mindfulness and the degree to which respondents’ experience thoughts and feelings. Pre, post  Measure of Current Status (MOCS) ; assesses current self-perceived status on the ability to relax at will, recognize stress-inducing situations, restructure maladaptive thoughts, be assertive about needs, and choose appropriate coping responses as needed. Pre, post

The *GetActive+* program will be conducted either virtually or in person (depending on patients’ preferences) by trained staff (psychologist or nurse practitioner, or both depending on availability) over the course of 10 weekly sessions. It is important that all eligible patients be able to participate should they choose to enroll. Thus, participants that wish to attend virtually but do not have the appropriate technology will be provided with a smart device, the type of which will be dependent on study funds and device availability. Prior to or directly after each session, participants will have the option to attend a 5-10 minute 1-on-1 medical check-in with the nurse practitioner. The purpose of these check-ins is to ensure that participants feel

physically safe and comfortable with the activity-based component of the program throughout the duration of their participation. Each of the 10 sessions will last approximately 60-minutes. Group sizes will be approximately 3-10 participants, however, this may be subject to change depending on the rate of attrition. Currently, we estimate approximately 20% attrition with the understanding that participant retention for this population might be less than what was observed in prior trials with *GetActive*. The interventionist will be trained by [name] and [name] and supervised weekly.

The *GetActive* + program used in the open pilot, will incorporate mind-body skills, cognitive behavioral and physical restoration skills (e.g., quota-based pacing) to help individuals increase self-reported, performance based and objective (step count) physical function. This program will teach participants four core skills: 1) weekly goal setting for gradual increase in time spent walking paired with activities of daily living that are meaningful and important to participants (i.e. walk instead of drive to the store; walk to the park with kids) 2) quota-based pacing (increasing walking goal gradually non-contingent of pain); 3) mind-body skills (e.g., diaphragmatic breathing to manage intense pain flares and pain anxiety; body scan to increase body awareness and reduce reactivity to pain sensations; mindfulness exercises to understand the transience of pain and change one's relationship with it; self-compassion when falling short of set goals); and 4) understanding the disability spiral (e.g. how reducing activity perpetuates pain and disability), correcting myths about pain or automatic pain-related thoughts that interfere with meeting program goals. Throughout the 10-week program, participants will be encouraged to increase their time spent walking each week. As in prior mind-body and activity studies, the RA will determine a new walking goal weekly based on whether the open pilot participant met their walking goal in the prior week. Each week participants will increase their activity goal by 10%-20% if they met their prior goal, maintain the same goal if they did not meet it, or decrease the goal by 10%-20% if they did not meet their goal for 2 consecutive weeks. Any risks due to walking will be controlled and monitored by the clinician during the first 20 minutes of each session. The clinician will do so by discussing with each participant how walking went in the week prior, troubleshooting any barriers to walking safely, and coming up with an individualized walking plan for the coming week. Participants will have the opportunity to provide informal feedback on the manual and content throughout the study.

Participants will be encouraged to complete their homework (logs for mind-body practice, physical activities) each day. Participants will be given the option to receive homework and session reminders via text messages from study staff. This between-session contact will focus on increasing treatment adherence, maintaining engagement, and session reminders. Specifically, Twilio will be used to send session reminders, reminders to practice program skills, and for links to home practice surveys using a standardized protocol. Twilio is an MGH-approved smartphone app that participants will have the option to consent to using. Text messages will be sent once or twice a week for the duration of the study, for participants who expressed interest in receiving text messages. Participants may opt-out of text message reminders at any point. See Table 3 for details of each program session.

Table 3. Session Content for *GetActive*+

Session	Topic	Skills
---------	-------	--------

Session 1	Live Well with Pain	Deep breathing
Session 2	Outsmarting the Pain	Catching unhelpful thoughts, quota-based pacing
Session 3	Becoming Away	Mindfulness, body scan
Session 4	Staying Engaged with your Life	Mindful walking, meaningful activities
Session 5	Working with Unhelpful Thoughts	Identifying and challenging Negative Automatic Thoughts (NATs)
Session 6	Staying in the Upward Spiral	Skill review
Session 7	Caring for Yourself When in Pain	Self-compassion, mindfulness of pain
Session 8	Feeling Connected with Others	Social connectedness, reducing loneliness
Session 9	Promoting Acceptance	Acceptance
Session 10	Staying on Track and Maintaining Your Progress	Maintenance skills

All participants will wear ActiGraph devices to monitor activity levels for 7-10 days after their baseline assessment and post-intervention assessment. Following the baseline assessment period, participants will return the ActiGraph device either in person at their first group session or mail the device back to study staff if they will be attending group sessions virtually. The post-intervention assessments will be scheduled to take place approximately 3 days after the last group session (e.g., Session 10). Participants will receive their ActiGraph device and wear it for the following 7-10 days. Participants will return their ActiGraphs via pre-paid envelopes provided by study staff. Participants will also be given the option to share contact information with the other group members following the post-program assessments. This is an optional procedure for those interested in staying in touch following group sessions.

Only trained study staff will have access to the data collected at baseline and post-program. Participants' data will be identified by an ID number only, and a link between names and ID numbers will be password-protected and kept separately. The information on the ActiGraph accounts will be password protected and only the study staff and patient will have access to that information. Training sessions will be audio-recorded and reviewed to ensure fidelity. All group sessions will be audio-recorded. Recordings will be used for weekly clinical supervision (e.g., problem solve challenging cases), and to assess study therapist's competency and fidelity to the content of each session. All study staff will have up to date Collaborative Institutional Training Initiative (CITI) certifications. All study procedures will be conducted using our published methodology.

Following the conclusion of the program, patients will have the option to participate in an exit interview. These interviews will be conducted utilizing procedures outlined by Krueger and guided by a semi-structured IRB approved interview guide. The goal of these interviews will be to understand the experiences of participants and garner feedback on the program. This feedback will eventually be used to further optimize the *GetActive+* program for use in future studies. Participants will be able to choose whether they would like to attend the exit interview in person

or remotely (i.e., over Zoom). In the event that exit interviews are conducted virtually, we will use an MGB Zoom account. Zoom specifically states that their software is equipped to keep information secure, and the software does not have access to identifiable information. Zoom is HIPPA compliant, MGB approved, and the current video software standard for patient care within our Department of Psychiatry. We will audio record the focus groups with consent from participants using MGB encrypted devices. We will transcribe recordings after each group and use these transcriptions to conduct qualitative analyses. No PHI will be included in the transcriptions. Outcomes will be used to guide subsequent manual adaptations and protocol, training, and fidelity procedures for the *GetActive+* program.

At the end of study enrollment (e.g., no longer recruiting/enrolling participants or conducting follow-ups with participants), we will conduct open-ended focus group or individual interviews with up to 20 participants who have completed the study. These group or individual interviews will be used to inform the future development of the program and to understand ways to better teach session content to increase understanding and engagement. Participants will be selected based on clinician perception on improvement and benefit and ability to engage in the material in a meaningful way. Interested participants will verbally consent after receiving a study fact sheet. Since we will be pulling from individuals who previously enrolled, we will only be re-consenting individual who choose to participate. We will contact participants via phone to gauge interest in participating, and the focus groups or individual interviews will be conducted in-person for up 60 minutes. We will be compensating participants an additional \$40 for their participation.

Our primary outcomes for the open pilot will be the feasibility, acceptability, and fidelity of the *GetActive+* program. Preliminary effectiveness outcomes will also be examined (e.g., multimodal physical function (self-report, 6-minute walk test and activity level measured via ActiGraph) and emotional function (depression and anxiety)).

Participants will be compensated \$60 for completing the baseline visit and up to \$100 for the 7–10-day baseline ActiGraph assessment (e.g., \$10 per day up to 7-days; additional \$30 for 7 days of complete and valid data). Participants will also receive up to \$150 worth of travel compensation (e.g., if sessions are in person, \$15 per session for 10 sessions). If participants attend group sessions virtually, they will not be subject to the compensation associated with transportation. To incentivize long-term engagement with the program, participants will receive a \$50 bonus for attending at least 8 of the 10 sessions. Participants will also receive \$100 for the completion of the post-program assessments and up to \$155 for the post-program ActiGraph data collection period (e.g., \$15 per day up to 7-days; additional \$50 provided for 7 days of complete and valid data). In addition to all the above, participants will be given the opportunity to earn \$40 for attending an in-person post-program exit interview (\$25 for remote exit interviews). Select participants (based on randomization and interest) can also receive \$40 for an additional focus group. Payments will be submitted and sent to participants following each major time point (i.e., baseline, final group session, and post-program exit interview). Overall, participants of the open pilot will earn up to \$695.

All study procedures for Spanish speaking groups will be identical to English groups. Participant interactions will be in Spanish through a native Spanish speaking RA and group facilitator (i.e., a native Spanish-speaking social worker). Spanish speaking study staff will be fully trained in the

GetActive+ intervention and study procedures. All study materials are translated and spot check by a Spanish speaking RA.

## **7. Risks and Discomforts**

### **Potential Risks & Protections Against Risks**

We anticipate minimal risk to subjects due to their participation in this study; however, some risks are associated with conducting the study. Potential risks are: (a) loss of confidentiality and (b) potential feelings of distress while completing assessments or participating in the open pilot. Participants may find it inconvenient to participate in the open pilot. Additionally, participants may experience muscle soreness as they increase walking, and this will be discussed, as part of the program, as normal. Following a quota-based pacing regimen will also help minimize this risk because activity will be increased gradually. All participants will be cleared for participation by their medical doctor. There is no risk associated with wearing the ActiGraph other than possible inconvenience. Special attention will be paid to the fact that we are asking older adults to walk. We will ensure that we help identify appropriate spaces to walk, use the Buddy system when applicable (older adults walk with friends or family), and monitor any side effects (e.g., injuries, falls) (See section 6).

#### **Loss of confidentiality**

A potential risk is the loss of confidentiality. In order to protect confidentiality, data will be identified only by subject codes, with all identifying information removed. The identity of patients will not be revealed in the presentation or publication of any results from the project. All study personnel will be educated about the importance of strictly respecting patients' rights to confidentiality and will fulfill the required HIPAA training. This study will be conducted in compliance with HIPAA and IRB guidelines on privacy and confidentiality in order to strictly respect and safeguard participants' confidentiality. All identifying data will be stored in locked or password protected files only accessible by study staff. All research data will be identified only by subject codes and identifying information will be removed. The code key connecting IDs to identifying information will be kept in a separate, secure and password protected location. Data in databases will be similarly identified only by coded ID number and will be stored in password protected drives and devices. We have extensive experience in strictly respecting patients' rights and maintaining confidentiality and do not anticipate any breach of confidentiality occurring during the present proposal. Participants will be informed about these risks and told that they may withdraw from the study and have their data removed from the study database at any time.

#### **Experiences of distress while completing assessments**

Throughout the course of the open pilot, it is possible that participants experience distress during group visits and/or home practice. In the unlikely event that a participant is determined to be in distress or actively suicidal and at risk for self-harm during any study procedure study staff will intervene. We will use a standardized protocol for assessing and monitoring risk developed by

[name] that has been successfully used in other trials. Alternatively, in event that suicidality is determined during one of the open pilot group sessions, the study clinicians will contact the PI immediately. We are hoping to avoid this scenario by excluding patients after screening who endorse suicidality or who have untreated severe mental health conditions that would require a higher level of care. We do not expect this unlikely event to occur, as there have been so such occurrences in our previous studies.

It is also important to note that participation this study does not involve treatment or diagnosis. However, it is possible that we may detect previously unknown problems during the open pilot group sessions or from the assessments. If any potential abnormality or medical problem is detected during the course of the study, the participant will be provided with an appropriate referral for medical follow-up. There is some risk of distress associated with the detection of a potential abnormality or medical problem.

Some participants may feel uncomfortable about the exit interviews being taped and transcribed. However, participation in exit interview will be optional. The purpose of the taping will be explained, confidentiality will be maintained, and verbal consent for taping will be obtained.

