4. In-Clinic Approaches by Study Staff: An RA will facilitate patient recruitment via in-clinic approaches. These approaches will ideally be informed through precursory eligibility assessments made by the RA based on the patient's medical record. If time restrictions do not allow for precursory eligibility assessments, the RA will consult RHC staff regarding their patient recommendations. The trained RA will then approach the patient and ask if they can introduce the study and answer any related questions. If patients indicate they are interested in participating, they will be guided through eligibility screening with the RA in person at RHC, or later on over the phone if the participant expresses interest but cannot be screened at that time. A baseline visit will be conducted in person.

At the conclusion of all screenings, the RA will gather patient availability for the in-person baseline assessment and the 10-week *GetActive+* program and email, mail or hand a copy of the informed consent form to participants. This will allow potential participants ample time to review the consent form prior to the baseline visit. All patients will be instructed not to sign it until they undergo formal consent at the in person visit. The recruitment strategies described above are informed by recommendations from RHC staff and are supported by [REDACTED]. Patients who choose to provide their consent will do so electronically (i.e., eConsent) in the presence of the research assistant to ensure that all questions or concerns associated with participation are answered. Consent will be collected via REDCap, a validated password-protected signature platform approved by MGB. They will receive a signed paper or digital copy of the informed consent form. All participants will be notified that their participation in the following open pilot is voluntary and that they are able to withdraw at any time. All study

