**Inclusion Criteria:**

1. Older Adults (i.e., age  $\geq 55$ , since aging is accelerated by impoverished lifestyles)
2. Has diagnosed musculoskeletal chronic pain of any type (e.g., pain duration  $> 3$  months)
3. Pain score  $\geq 4$  (moderate) on the Numerical Rating Scale
4. Cognitively able to participate as measured by the Short Portable Mental Health questionnaires (e.g.,  $< 4$  errors)
5. No self-reported current active, untreated psychotic or substance use disorder that would interfere with participation in the research study
6. Self-reported ability to complete the 6-minute walk test
7. Patient at RHC who is cleared for participation by medical staff
8. English or Spanish fluency.

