**Exclusion Criteria:**

1. Current serious medical illness that is expected to worsen in the next 6 months (e.g., cancer)
2. Individuals who are unwilling or unable to wear the ActiGraph device

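### Section 7 relies on excluding patients for suicidality or severe untreated mental illness, but the Section 4 eligibility criteria contain no such exclusion

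*Combined protocol and SAP*

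**What the plan says.** Section 7 (Risks and Discomforts), under distress while completing assessments, describes how staff respond if a participant is distressed or suicidal during the study. It then says the team hopes to prevent this by "excluding patients after screening who endorse suicidality or who have untreated severe mental health conditions that would require a higher level of care".

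Section 4 (Subject Selection) sets out eligibility as 8 inclusion and 2 exclusion criteria. Those closest to the Section 7 rule are:

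- Inclusion 4: "Cognitively able to participate as measured by the Short Portable Mental Health questionnaires", with a limit on the number of errors.
- Inclusion 5: "No self-reported current active, untreated psychotic or substance use disorder that would interfere with participation in the research study".
- Inclusion 7: "Patient at RHC who is cleared for participation by medical staff". Section 7 repeats that every participant will be medically cleared.

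The two exclusion criteria concern serious physical illness expected to worsen within 6 months, and "Individuals who are unwilling or unable to wear the ActiGraph device".

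For in-clinic recruitment, Section 4 also describes a check of the medical record before the patient is approached: "These approaches will ideally be informed through precursory eligibility assessments made by the RA". The fallback is: "If time restrictions do not allow for precursory eligibility assessments, the RA will consult RHC staff regarding their patient recommendations".

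**The concern.** Section 7 offers this exclusion as a protection for participants, and as the stated means of keeping suicidality from arising in sessions. A protection of that kind works only if the people who decide eligibility apply it, and the list they would use is in Section 4. If the rule is absent there, it has no stated criterion, no method of ascertainment and no step responsible for it.

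The two sections can then give different answers for the same patient. Someone who meets all 10 criteria could be enrolled by staff working from Section 4 and turned away by staff working from Section 7. Because the point concerns participant safety, the protocol should state the rule once and consistently.

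**Working it through.** No formula applies. The check compares the two texts and counts.

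**Step 1. Split the Section 7 rule into its parts.** It has two grounds: (a) the patient endorses suicidality; (b) the patient has a severe mental health condition that is untreated and calls for a higher level of care.

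**Step 2. Compare each Section 4 criterion with (a) and (b).**

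| Criterion | Subject | Covers (a)? | Covers (b)? |
|---|---|---|---|
| Inclusion 1 | Age | No | No |
| Inclusion 2 | Chronic pain diagnosis | No | No |
| Inclusion 3 | Pain score | No | No |
| Inclusion 4 | Cognitive ability, scored in errors | No | No |
| Inclusion 5 | Psychotic or substance use disorder | No | In part, with a different test |
| Inclusion 6 | Ability to do the walk test | No | No |
| Inclusion 7 | Medical clearance | Not stated | Not stated |
| Inclusion 8 | Language | No | No |
| Exclusion 1 | Worsening medical illness | No | No |
| Exclusion 2 | Wearing the activity monitor | No | No |

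The count is 8 + 2 = 10 criteria. Those mentioning suicidality: 0 of 10. Those using a higher-level-of-care test: 0 of 10. Those naming psychiatric disorders: 1 of 10. Inclusion 4 refers to a questionnaire with mental health in its name, but uses it only for cognition.

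**Step 3. Is inclusion 5 a paraphrase of ground (b)?** No. It covers two types of disorder, whereas Section 7 covers any severe condition. It rests on self-report, which Section 7 does not specify for this ground. It asks whether the disorder would interfere with participation, whereas Section 7 asks about level of care. The two overlap without coinciding. A patient with a severe untreated condition that is neither psychotic nor substance-related passes inclusion 5 and may still fall under Section 7.

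**Step 4. Does any other described step apply the rule?**

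- Medical clearance applies to every participant, but no mental health ground is given for it.
- The record review is described for 1 of the 4 numbered recruitment routes (flyers, Rally post, provider referrals, in-clinic approaches). It is qualified by *ideally*, has a fallback, and is not said to apply the Section 7 exclusion on any route.
- The recruitment, screening and enrolment text in Sections 4 and 5 describes no question about suicidality.
- The baseline measures in Section 6 and Table 2 are completed only after consent and enrolment, so they are not eligibility checks.
- The standardized risk protocol in Section 7 is described for events during study procedures.

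**Step 5. Search the whole document.** The stem *suicid* occurs 3 times, all in the same subsection of Section 7.

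**The case against.** The best case on the other side is that this is an omission and not a contradiction. Section 4 nowhere says that such patients are eligible and does not call its list exhaustive; Section 7 adds a restriction, and staff who read the whole protocol can honour both. Section 4 also uses *after screening* for the ordinary outcome of being found ineligible, so Section 7 may simply be describing a result of eligibility screening. Every participant must be medically cleared, and it cannot be assumed that clinicians giving clearance would ignore serious mental illness. The screening form is not reproduced and may ask about suicidality. After enrolment, chart review, self-reported mental health history and the depression and anxiety measures are further points at which such patients might be identified.

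Much of this stands as a limit on the consequence. Actual enrolment of such a patient depends on an unseen form and on unstated grounds for clearance. The reading of *after screening* as a screening outcome is fair, and on that reading the rule belongs all the more clearly in the eligibility list. None of it removes the mismatch. A full list of criteria that leaves out an exclusion relied on elsewhere does not state the same rule, and no described step is said to supply the missing part. The measures taken after consent come too late to decide eligibility.

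**Conclusion.** The concern holds. Suicidality is wholly absent from the eligibility list, and the second ground is covered only in part, by one criterion with a different scope and test. Applying Section 4 as written could enrol patients whom Section 7 says are excluded: those who endorse suicidality, or who have a severe untreated condition other than a psychotic or substance use disorder that calls for a higher level of care.

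Confidence is high for the textual mismatch and does not extend to what the screening form contains. The documents give no prevalence, so no number of affected participants, out of up to 50, is estimated. The in-study response to distress or suicidality does not depend on the exclusion and remains in place. No analysis, sample-size statement or go/no-go benchmark is shown to be affected.

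**What to change.** Reconcile the inclusion and exclusion lists in Section 4 with the distress subsection of Section 7 so that they state the same rule, and name the screening step that applies it. If medical clearance under inclusion 7, or the record review before in-clinic approaches, is meant to be that step, say so in both places. What the rule should be clinically is for the investigators to decide.

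The cost is a short wording amendment to Section 4, Section 7 or both. The screening form needs changing only if it does not already apply the reconciled rule.
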